1.1.5.2 Disposition of Subjects in the Entire Study

Analysis set:	All subjects who were randomized	
Analysis variables:	Study drug administration status	[Not treated]
	Reason for not being treated	[Pretreatment event/Adverse event, Significant protocol deviation, Lost to follow-up, Voluntary withdrawal, Study termination, Pregnancy, Lack of efficacy, Other]
	Study drug completion status	[Completed, Incompleted]
	Reason for not being completed	[Pretreatment event/Adverse event, Significant protocol deviation, Lost to follow-up, Voluntary withdrawal, Study termination, Pregnancy, Lack of efficacy, Other]
	Completion status of the follow-up period	[Completed, Incompleted]
	Reason for not being completed	[Pretreatment event/Adverse event, Significant protocol deviation, Lost to follow-up, Voluntary withdrawal, Study termination, Pregnancy, Lack of efficacy, Other]

Analysis methodology: The following analysis will be performed for the above analysis variables by each treatment group and in the consolidated treatment groups. When calculating percentages of the reasons for not being treated, the number of subjects who did not receive the study drug will be used as the denominator. When calculating percentages of the reasons for not being completed, the number of subjects who did not complete the study drug/follow-up period will be used as the denominator.

(1) Frequency distribution

1.1.6 Study Drug Completion Status

Analysis set:	All subjects who were randomized	
Analysis variables:	Study drug completion status	[Completed, Incompleted]
	Reason for not being completed	[Pretreatment event/Adverse event, Significant protocol deviation, Lost to follow-up, Voluntary withdrawal, Study termination, Pregnancy, Lack of efficacy, Other]
Categories:	Number of study drug administrations	[0, 1-4, 5-8, 9-12, 13-24, 25-36, 37-48, 49-52, 53-Max]
Analysis methodology:	
The following analysis will be performed for the above analysis variables by each treatment group and in the consolidated treatment groups.
 
(1) Frequency distribution by number of study drug administrations
	

1.1.7 Protocol Deviations and Analysis Sets

1.1.7.1 Protocol Deviations

Analysis set:	All subjects who were randomized	
Analysis variables:	Protocol deviations	[Major GCP violations, Deviations of protocol entry criteria, Deviations of discontinuation criteria, Deviations related to treatment procedure or dose, Deviations concerning excluded medication or therapy, Deviations to avoid emergency risk, Other]
Analysis methodology:	
The following analysis will be performed for the above analysis variables by each treatment group and in the consolidated treatment groups.
 
Frequency distribution of subjects with protocol deviations will be provided for each deviation category above. A subject who has several deviations that can be classified into the same category will be counted once in each appropriate category (overlapped counting).
 
(1) Frequency distribution
	

1.1.7.2 Analysis Sets

Analysis set:	All subjects who were randomized	
Analysis variables:	Handling of subjects and subject data in analysis sets	[Categories are based on the specifications in “Handling Rules for Analysis Data”]
Inclusion/Exclusion of analysis sets		
	Full analysis set	[Included]
	Per protocol set	[Included]
	Safety analysis set	[Included]
Analysis methodology:	
The following analyses of (1) and (2) will be performed for the above analysis variables by treatment group and the following analysis of (3) will be performed by each treatment group and in the consolidated treatment groups.
 
A subject who corresponds to several categories in (1) and (2) will be counted once in each appropriate category (overlapped counting).
 
 (1) Frequency distributions concerning the handling of subjects in each analysis set (2) Frequency distributions concerning the handling of subject data in each analysis set (3) Frequency distributions concerning the number of subjects included in each analysis set 	

1.2 Demographic and Other Baseline Characteristics

1.2.1 Distribution of Baseline Demographics

Analysis set:	All subjects who were randomized	
Analysis variables:	Age (years)	[Min \leq - <65, 65 \leq - \leq Max]
		[Min \leq - <75, 75 \leq - \leq Max]
	Sex	[Male, Female]
	Height (cm)	
	Weight (kg) (Week 0)	
	BMI (kg/m ²) (Week 0)	[Min \leq - <18.5, 18.5 \leq - <25.0, 25.0 \leq - <30.0, 30.0 \leq - \leq Max]
	Duration of disease (months)	[Min \leq - \leq 24, 24< - \leq 60, 60< - \leq 120, 120< - \leq Max]
	Smoking status	[Never smoked, Current smoker, Ex-smoker]
	Alcohol use	[Yes, No]

Exercise therapy	[Yes, No]
Hemodialysis	[Yes (end-stage renal failure), No (severe renal impairment)]
Use of antidiabetic drugs (Week -6)	[Yes, No]
Rapid-acting insulin	[Yes, No]
secretagogues	
Details of rapid-acting insulin secretagogues	
Mitiglinide calcium hydrate	[Yes]
Repaglinide	[Yes]
α -glucosidase inhibitors	[Yes, No]
Details of α -glucosidase inhibitors	
Acarbose	[Yes]
Miglitol	[Yes]
Voglibose	[Yes]
Insulin preparations	[Yes, No]
Types of insulin preparations	[Mixed, intermediate-acting, Long-acting soluble]
Reason for concomitant use of antidiabetic drugs being judged to be appropriate	[Combination therapy is expected to be more effective, Development of AEs due to dose increase is concerned, Maximum dose has already been administered, Other]
Creatinine (mg/dL) (Week 0)	Male
Male	[Min \leq - \leq 2.4, 2.4 $<$ - \leq Max]
Female	Female
	[Min \leq - \leq 2.0, 2.0 $<$ - \leq Max]
Creatinine clearance (mL/min) (Week 0)	
eGFR (mL/min/1.73 m ²) (Week 0)	[Min \leq - $<$ 15, 15 \leq - $<$ 30, 30 \leq - \leq Max]
HbA1c (%) (Week 0)	[Min \leq - $<$ 7.0, 7.0 \leq - \leq Max]
	[Min \leq - $<$ 8.0, 8.0 \leq - \leq Max]

Fasting blood glucose (mg/dL) (Week 0)	[Min≤ - <130, 130≤ - <160, 160≤ - ≤Max]
Glycoalbumin (%) (Week 0)	[Min≤ - <24, 24≤ - ≤Max]
Fasting C-peptide (ng/mL) (Week 0)	[Min≤ - <1.0, 1.0≤ - <2.0, 2.0≤ - ≤Max]
Fasting glucagon (pg/mL) (Week 0)	
DPP-4 activity (nmol/min/mL) (Week 0)	
Analysis methodology:	The following analysis will be performed for the above analysis variables by each treatment group and in the consolidated treatment groups. (1) Frequency distributions for categorical variables and summary statistics for continuous variables

1.2.2 Medical History and Concurrent Medical Conditions

Analysis set:	Safety analysis set
Analysis variables:	Medical history Concurrent medical conditions
Analysis methodology:	The following analysis will be performed for the above analysis variables by each treatment group and in the consolidated treatment groups. The analysis variables will be coded using MedDRA dictionary and will be summarized based on the SOC and PT. SOC will be sorted alphabetically and PT will be sorted in decreasing frequency. (1) Frequency distributions for medical history (by SOC and PT) (2) Frequency distributions for concurrent medical conditions (by SOC and PT) The frequency distributions will be provided according to the rules below: [Number of subjects] A subject with multiple occurrences of medical history or concurrent medical condition within a SOC will be counted only once in that SOC. A subject with multiple occurrences of medical history or concurrent medical condition within a PT will be counted only once in that PT.

1.2.3 Medication History and Concomitant Medications

Analysis set:	Safety analysis set
---------------	---------------------

Analysis variables: Medication history
Concomitant medications

Analysis methodology: The following analysis will be performed for the above analysis variables by each treatment group and in the consolidated treatment groups.
The analysis variables will be coded by use of WHO Drug and summarized based on Preferred Name, which will be sorted in decreasing frequency.
A subject who has been administered several medications with the same Preferred Name will be counted only once for that Preferred Name.

- (1) Frequency distributions for medication history
- (2) Frequency distributions for concomitant medications that were discontinued prior to the first dose of the study drug
- (3) Frequency distributions for concomitant medications that were ongoing at the first dose of the study drug and continued in the treatment period
- (4) Frequency distributions for concomitant medications that started after the first dose of the study drug
- (5) Frequency distributions for concomitant medications that were ongoing at the first dose of the study drug and continued in the treatment period, and concomitant medications that started after the first dose of the study drug

1.2.4 Concomitant Antidiabetic Drugs Permitted in the Study

Analysis set: Full analysis set

Analysis variables: Newly added oral hypoglycemic drug [Yes, No]
in Treatment Period II (at Week 16
and thereafter)
Any change in antidiabetic drugs that [Yes, No]
are being used at Week -6 and will be
concomitantly used during the study
period in Treatment Period II

Stratum: Types of antidiabetic drugs [Rapid-acting insulin
secretagogues,
 α -glucosidase inhibitors,
Insulin preparations]

Analysis methodology: The following analysis will be performed for the newly added oral hypoglycemic drug in Treatment Period II (at Week 16 and thereafter) in subjects who are not using any antidiabetic drug at Week -16 among the full analysis set by treatment group. Also, the following analysis will be performed for any change in antidiabetic drugs that are being used at Week -6 and will be concomitantly used during the study period in Treatment Period II in subjects who are using antidiabetic drugs at Week -16 among the full analysis set by treatment group. Treatment Period II is the period from the start of the study drug administration for Treatment Period II until 20 days after the last administration of the study drug for Treatment Period II.

(1) Frequency distribution

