6.0 STUDY DESIGN AND DESCRIPTION

6.1 Study Design

This is a phase 3, multicenter, randomized, double-blind, placebo-controlled, parallel-group, comparative study (Treatment Period I) and a phase 3, multicenter, open-label, long-term study (Treatment Period II) using placebo as a control to evaluate the efficacy and safety of SYR-472 when administered orally at a dose of 25 mg once weekly in patients with type 2 diabetes mellitus complicated by severe renal impairment or end-stage renal failure and with inadequate glycemic control despite diet and/or exercise therapy (if any) or despite treatment with 1 antidiabetic drug (Table 6.a) in addition to diet and/or exercise therapy (if any).

Table 6.a Concomitant Antidiabetic Drugs Permitted in the Study

Type	Drug Name (Nonproprietary Name or Class)
Rapid-acting insulin secretagogues	Mitiglinide calcium hydrate, repaglinide
α -glucosidase inhibitors	Acarbose, miglitol, voglibose
Insulin preparations	Mixed, intermediate-acting, or long-acting soluble insulin (40 units/day or less*)

*: For change in the dosing unit of insulin preparations, see 2 (2) in Section 7.3.

[figure not shown]
Subjects who enter the screening period after signing informed consent and are considered eligible according to the inclusion and exclusion criteria will be randomly assigned to either of the SYR-472 25 mg group or placebo group. Subjects who are assigned to the SYR-472 25 mg group in Treatment Period I will continue to be treated with SYR-472 25 mg in Treatment Period II, while those assigned to the placebo group will be switched to SYR-472 25 mg in Treatment Period II.

In Treatment Period I, 1 SYR-472 25 mg tablet or placebo tablet will be orally administered once weekly before breakfast. In Treatment Period II, 1 SYR-472 25 mg tablet will be orally administered once weekly before breakfast.

The study period consists of 6 weeks of screening, 52 weeks of treatment, and 2 weeks of follow-up, a total of 60 weeks. The treatment period consists of Treatment Period I (double-blind) between Week 0 and Week 12 and Treatment Period II (open-label) between Week 12 and Week 52. Subjects will visit the site at the start of the screening period (Week -6), Week -2 of the screening period, end of the screening period (Week 0), Week 2 and Week 4 of the treatment period, and at every 4 weeks until Week 52 of the treatment period, and at the end of the follow-up period (Week 54) (total of 18 visits).

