- For subjects who are not using any other antidiabetic drug in Treatment Period I (those who are only treated with the study drug), the use of 1 new oral hypoglycemic drug* is allowed at Week 16 of the treatment period and thereafter.

*: Any 1 of the following medications: metformin, repaglinide, acarbose, miglitol, or voglibose

(2) Insulin Preparations

For subjects who are receiving insulin preparations at the start of the screening period (Week -6) and continue to receive in the study period, insulin preparations should be administered as specified below.

• Type of Insulin Preparation

Any 1 of the mixed (rapid-acting or ultrarapid insulin containing no more than 30% of volume), intermediate-acting, or long-acting soluble insulin preparations should be used alone, and should not be changed throughout the study period.

• Daily Dose (Unit) of Insulin Preparation

1) Screening Period

The daily dose (unit) of insulin preparation should be 40 units/day or less at the start of the screening period (Week -6), and the dose and regimen should not be changed during the screening period (for subjects on hemodialysis who receive different daily doses [unit] of insulin preparation on days of hemodialysis and on other days, each dose and regimen of insulin preparation should not be changed).

2) Treatment Period I

The dose and regimen of insulin preparations at the start of the screening period (Week -6) should be maintained and no changes will be allowed, in principle.

However, the investigator or sub-investigator should consider reduction or increase in the daily dose (unit) of insulin preparation if the criteria described below are met. After dose reduction or increase, the unit after reduction or increase should be continued.

Even if reduction in the daily dose (unit) of insulin preparation results in the discontinuation of insulin use, the study may be continued. If increase in the daily dose (unit) of insulin preparation results in a dose exceeding 40 units/day on a continuing basis, the investigator or sub-investigator should determine whether the study should be continued or discontinued, with respect to the safety of the subject.

Criteria for dose reduction: If either criterion (i) or (ii) described below is met, the daily dose (unit) of insulin preparation may be reduced from the unit administered at the start of the screening period (Week -6) by up to 4 units (regardless of the number of changes).

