9.1.2 Demographics, Medical History, and Medication History Procedure

Demographic information to be obtained will include date of birth, sex, height, weight, body mass index (BMI), alcohol use, smoking status, onset time of type 2 diabetes, presence or absence of hemodialysis and diet and/or exercise therapy.

The BMI will be calculated by the sponsor using the formula provided below:

Metric: $BMI = \text{weight (kg)} / [\text{height (m)}]^2$

Height should be measured in centimeters without decimal places (rounding off the first decimal place). For measurement of weight, refer to Section 9.1.5.

Medical history to be obtained will include determining whether the subject has any significant conditions or diseases relevant to the disease under study that stopped within 1 year prior to signing of informed consent. Ongoing conditions are considered concurrent medical conditions (see Section 9.1.8).

Medication history information to be obtained includes drug name, route of administration, daily dose, and end date of any antidiabetic drug stopped between 24 weeks prior to the end of the screening period (Week 0) and the start of the screening period (Week -6).

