9.1.3 Antidiabetic Drugs Administered During the Study

1. Screening Period

CONFIDENTIAL

For antidiabetic drugs administered at the start of the screening period (Week -6) and concomitantly used during the study period, the drug name, type (for insulin preparations), and daily dose of antidiabetic drugs used at the start of the screening period (Week -6) and concomitantly used during the study will be recorded in the eCRF.

2. Treatment Period I

For antidiabetic drugs administered at the start of the screening period (Week -6) and concomitantly used during the study period, the drug name, type (for insulin preparations), and daily dose of antidiabetic drugs used at the start of the screening period (Week -6) and concomitantly used during the study period will be recorded in the eCRF.

In case concomitant use of other antidiabetic drugs in addition to an antidiabetic drug used at the start of the screening period (Week -6) is judged to be appropriate, the investigator or sub-investigator should record the reason for the judgment in the eCRF according to the following categories:

- Combination therapy is expected to be more effective.
- Development of AEs due to dose increase is concerned.
- The maximum dose has already been administered.
- Others

3. Treatment Period II

For subjects who do not receive 1 antidiabetic drug other than the study drug in Treatment Period I and start the administration of 1 new oral hypoglycemic drug from Week 16 of the Treatment Period II (or thereafter), the drug name, daily dose, date of the start and end of administration, will be recorded in the eCRF.

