1.3.2 Compliance of Antidiabetic Drugs

Analysis set: Full analysis set

Analysis variables: Compliance with antidiabetic drugs [Fully complied (90% or more), Almost complied (70% or more), Occasionally complied (50% or more), Rarely complied (less than 50%)]

Visits: Weeks -2, 0, 2, 4, 8, 12, 16, 20, 24, 28, 32, 36, 40, 44, 48, 52 or at discontinuation, and 54

Analysis methodology: The following analysis will be performed for the above analysis variables in subjects who are using antidiabetic drugs at Week -16 among the full analysis set by each treatment group and in the consolidated treatment groups.

(1) Frequency distributions at each visit

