2.4.8 Examination of Subgroups

Analysis set:	Full analysis set
Analysis variables:	Change in HbA1c at the end of Treatment Period I from Week 0
Stratum:	
Age (years) [Min≤ - <65, 65≤ - ≤Max]
 
Sex [Male, Female]
 
BMI (kg/m²) (Week 0) [Min≤ - <25.0, 25.0≤ - <30.0, 30.0≤ - ≤Max]
 
Duration of disease (months) [Min≤ - ≤120, 120< - ≤Max]
 
Medication history [Yes, No]
 
Hemodialysis [Yes (end-stage renal failure), No (severe renal impairment)]

	
Use of antidiabetic drugs (Week -6) [Yes, No]
 
Rapid-acting insulin secretagogues [Yes, No]
 
α-glucosidase inhibitors [Yes, No]
 
Insulin preparations [Yes, No]

	
eGFR (mL/min/1.73 m²) (Week 0) [Min≤ - <15, 15≤ - ≤Max]
 
HbA1c (%) (Week 0) [Min≤ - <7.0, 7.0≤ - ≤Max] [Min≤ - <8.0, 8.0≤ - ≤Max]
 
Fasting blood glucose (mg/dL) [Min≤ - <160, 160≤ - =Max] (Week 0)

	
Glycoalbumin (%) (Week 0) [Min≤ - <24, 24≤ - ≤Max]
 
Fasting C-peptide (ng/mL) [Min≤ - <2.0, 2.0≤ - ≤Max] (Week 0)

Analysis methodology:	
The following analyses will be performed for the above analysis variables.
 
(1) Summary statistics and the two-sided 95% CI for the mean will be calculated for each stratum by treatment group, as well as the intergroup difference in the mean between treatment groups (SYR-472 25 mg/SYR-472 25 mg group – placebo/SYR-472 25 mg group) and the two-sided 95% CI.
 
(2) The ANCOVA will be performed for each stratum with the change in HbA1c at the end of Treatment Period I from Week 0 as the response and with treatment group, stratum, and

interactions of treatment group and stratum as factors. The stratum will be included in the ANCOVA model as category variables based on the above category and analyzed.

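### SAP 1.2.4 and 1.3.2 select subjects by drug use at Week -16, evidently a slip for Week -6; separately, the end-of-Treatment-Period-II row is in effect the last value on SYR-472 25 mg and should say so

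*SAP*

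**What the plan says.** **Drug-use selection.** SAP 1.2.4 has two tables. The first, on oral drugs added from Week 16 of treatment, is run "in subjects who are not using any antidiabetic drug at Week -16 among the full analysis set by treatment group". The second covers "any change in antidiabetic drugs that are being used at Week -6 and will be concomitantly used during the study period", but in subjects chosen by use at Week -16. SAP 1.3.2 runs the compliance table "in subjects who are using antidiabetic drugs at Week -16 among the full analysis set". Elsewhere the SAP classifies by Week -6: the stratum in 2.4.8 begins "Use of antidiabetic drugs (Week -6", and 1.2.1 and 3.1.3 use the same variable.

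**End-of-period row.** The SAP section on handling of time windows has an end-of-Treatment-Period-II row in six tables: HbA1c, fasting blood glucose, glycoalbumin, fasting C-peptide, glucagon with DPP-4 activity, and weight with BMI. Its scheduled day is Day 7 after the last SYR-472 25 mg tablet, and its window closes at follow-up Day 20. An asterisked footnote counts the opening of the window (Day 2 onward) from the first SYR-472 25 mg tablet instead of the first Period II dose. By the SAP's definitions, that first tablet falls in Period I for the SYR-472/SYR-472 group (SYR/SYR below) and in Period II for the placebo/SYR-472 group (placebo/SYR).

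**The concern.** The selection phrases in 1.2.4 and 1.3.2 are operative: they say who enters a table. A programmer who tried to follow them would sort subjects by their status ten weeks before the study first saw them. Some subjects could land in the wrong table, for example a subject with no baseline drug in a table of compliance with that drug.

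For the end-of-period row, the issue is what a reader of the output will think it shows. A row named for Treatment Period II can hold a Period I value in one group and not in the other. It feeds the by-group summaries in SAP 2.2.1 and 2.3.1 and the proportions below 6.0%, 7.0% and 8.0% HbA1c in 2.2.1.

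**Working it through.** The plan states no figure on this point, so the check compares passages and applies the window rule to example subjects.

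**Step 1: where Week -16 falls.** In days: -16 × 7 = -112; -12 × 7 = -84; -6 × 7 = -42. Protocol 6.1 puts the first visit at Week -6, and the earliest SAP window opens at Study Day -49. Week -16 is 112 - 42 = 70 days before the first visit.

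**Step 2: can use at Week -16 be derived?**
- Protocol 9.1.3 records the name, type (for insulin) and "daily dose of antidiabetic drugs used at the start of the screening period (Week -6"). No start date is listed.
- Protocol 9.1.2 records "drug name, route of administration, daily dose, and end date of any antidiabetic drug stopped between 24 weeks prior to" Week 0 and the start of screening. That gives an end date, again with no start date.
- A subject with no drug in either record can be called a non-user at Week -16. For a drug in use at Week -6, or one stopped after Week -16, the listed items do not show whether it had been started by Week -16.

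**Step 3: would a literal reading pick different subjects?** Inclusion criterion 7 fixes drug status only from 6 weeks before Week -6, that is Week -12. Status in the 112 - 84 = 28 days from Week -16 to Week -12 is open.
- A subject who stops a drug in that interval is untreated at Week -6 and belongs to the population that Protocol 7.3 allows an added oral drug. Read literally, the subject leaves the add-on table and enters the drug-change and compliance tables.
- A subject who starts a drug in that interval is misplaced the other way.

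With Week -6 in all three places, the selections agree with 1.2.1, 2.4.8 and 3.1.3.

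**Step 4: the end-of-Period-II row.** A value on Study Day d qualifies if (d - day of first SYR-472 tablet + 1) ≥ 2 and (d - day of last SYR-472 tablet) ≤ 20. The value nearest to 7 days after the last tablet is used. Samples are taken before dosing. Entries are the Study Day of the value used.

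| Case | SYR/SYR end of I | SYR/SYR end of II | Placebo/SYR end of I | Placebo/SYR end of II |
|---|---|---|---|---|
| A. Stops in Period I: last dose Day 50, sample Day 57 | 57 | 57 | 57 | none |
| B. Last Period I dose Day 78, one Period II dose Day 85, no sample after Day 85 | 85 | 85 | 85 | none |
| C. As B, with a termination sample on Day 92 | 85 | 92 | 85 | 92 |
| D. Completer: last dose Day 358, sample Day 365 | 85 | 365 | 85 | 365 |

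- Case A, SYR/SYR: 57 - 1 + 1 = 57 ≥ 2 and 57 - 50 = 7 ≤ 20, so the value qualifies. Placebo/SYR has no SYR-472 tablet.
- Case B, placebo/SYR: 85 - 85 + 1 = 1, below 2, so nothing qualifies. SYR/SYR: 85 - 1 + 1 = 85, so the Week 12 pre-dose value qualifies.
- Case C, placebo/SYR: 92 - 85 + 1 = 8 ≥ 2. Both groups now use a Period II value.
- Without the footnote, A and B would give no end-of-Period-II value in either group; C and D would not change.

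**The case against.** **On Week -16.** The slip corrects itself. The drug-change sentence names Week -6 too, and no other reading can be worked. A reader might infer that the tables will be built on the wrong subjects. The documents do not support that: because the literal status cannot be fully derived, a programmer would more likely raise a query than produce the table. This stands, and it is why the point is minor. It does not remove the need to correct a selection rule. A fault in reading the PDF cannot be excluded, but the same text in three places makes it unlikely.

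**On the end-of-period row.** The rule is explicit and disclosed. The row carries an asterisk, its scheduled day is anchored to the last SYR-472 25 mg tablet, and the safety analyses in SAP 3.1.1 likewise count from the start of that tablet. A placebo subject who stops in Period I has no value on SYR-472 to give, so the asymmetry follows from exposure. This stands as well. A reader might infer that the row is an error and should be limited to Period II; the documents fit a deliberate last-value-on-drug convention at least as well.

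Nor is case B routine. Protocol 9.3.4 asks for the Week 52 procedures within 7 days of the final dose whenever possible, which leads to case C. Case B needs a missed termination visit or a sample that is not evaluable.

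What remains is a mismatch between the row's name and its content.

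**Conclusion.** **Week -16** is wrong as written, with high confidence and minor consequence. It affects the two tables in SAP 1.2.4 and the one in 1.3.2, all descriptive.

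**The end-of-Period-II row** is a labelling point, held with lower confidence. The Handling Rules for Analysis Data, which decide which values are eligible, are not among the documents and may already limit such values.

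Neither point has a derivable size. The documents give no stopping rate for Period I. The nearest figure, about 53 randomized and 51 evaluable per group (Protocol 13.3), leaves 2/53 = 3.8% not evaluable for the primary endpoint, which is not a stopping rate. One carried Period I value is 1/53 = 1.9% of a group of 53. Its share is larger if fewer subjects contribute, as may happen in the HbA1c proportions, where SAP 2.2.1 can be read as admitting only subjects above the target at Week 0.

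A reader might also infer that the efficacy conclusion is at risk. It is not. The primary ANCOVA and the end-of-Period-I comparison do not use this row, the Week 16 to 52 by-visit rows do not carry the footnote, and the SAP plans no between-group difference for the end-of-Period-II row.

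**What to change.** 1. Replace Week -16 with Week -6 at both places in SAP 1.2.4 and in 1.3.2. This is one term in three places and needs no new data, since use at Week -6 is already recorded.
2. Keep the footnote rule and the row name, which also appears in Protocol 13.1.3. Add a note to each output that uses the row, including the HbA1c proportions, that it is the last value on SYR-472 25 mg. Report per group how many of the values come from Period I. The cost is one line of text and one count per table; Period II treated or not-treated status is already planned in SAP 1.1.5.1.
3. Limit the row to Period II values only in a supplementary summary, if one is wanted. That restriction is a trade-off: it removes SYR/SYR subjects who stop early, including for lack of efficacy or adverse events, and may make the long-term results look better.
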